2.7. Imputation Rules for Missing AE Date/Time of Onset/Resolution

Partial AE onset dates will be imputed as follows:

- If the onset date of an adverse event is missing day only, it will be set to:
 - First day of the month that the AE occurred, if month/year of the onset of AE is different from the month/year of the study drug start
 - The day of study drug start, if the month/year of the onset of AE is the same as month/year of the study drug start date and month/year of the AE resolution date is different
 - The day of study drug start or day of AE resolution date, whichever is earliest, if month/year of the onset of AE and month/year of the study drug start date and month/year of the AE resolution date are same
- If the onset date of an adverse event is missing both day and month, it will be set to the earliest of:
 - January 1 of the year of onset, as long as this date is on or after the study drug start date
 - Month and day of the study drug start date, if this date is the same year that the AE occurred
 - Last day of the year if the year of the AE onset is prior to the year of the study drug start date,
 - The AE resolution date.
- Completely missing onset dates will not be imputed.

Partial AE resolution dates not marked as ongoing will be imputed as follows:

• If the resolution date of an adverse event is missing day only, it will be set to the earliest of the last day of the month of occurrence of resolution or the day of the date of death, if the death occurred in that month.

- If the resolution date of an adverse event is missing both day and month, it will be set to the earliest of December 31 of the year or the day and month of the date of death, if the death occurred in that year.
- Completely missing resolution dates will not be imputed.

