2. GENERAL ANALYSIS DEFINITIONS

Study Day is calculated in reference to the date of randomization for efficacy analyses and date of first dose for safety analyses (efficacy analysis Study Day 1 = date of randomization; safety analysis Study Day 1 = date of first dose). Positive study days will count forward from Study Day 1. Study Day -1 will be the day before Study Day 1, and all subsequent negative study days will be measured backward from Study Day -1. There will be no Study Day 0.

The first dose starts on Day 1 of Cycle 1.

Unless otherwise specified, baseline value is defined as the closest measurement prior to the first dose of study drug. Change from baseline will be defined as (post-baseline value – baseline value).

Treatment Duration is calculated as the duration of time from the date of the first dose of study drug to the date of last dose of the study drug, ie, date of last dose – date of first dose + 1.

Time to Event is calculated as the number of days from randomization to the date of the event of interest, ie, date of event of interest – date of randomization + 1. Time to event endpoints will be based on the actual date of the event, not visit number or visit label.

Continuous/numerical variables will be summarized using mean, standard deviation (SD), median, minimum, and maximum. Categorical variables will be summarized using count and percentage. In general, means and other measures of central tendency will be displayed with one more decimal digit than collected, and standard deviations and other measures of variability will be displayed with two decimal digits more than collected. For frequency counts of categorical variables, categories for which the counts are zero will be displayed for the sake of completeness. For example, if no subject discontinued due to "withdrawal of consent", this reason would still be included in the table but with a count of 0.

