2.5. Study Day and Relative Day

Study Day 1 or Day 1 refers to the start of the first study drug administration for safety analysis or randomization date for efficacy analysis. All efficacy and safety assessments at all visits will be assigned a day relative to this date.

Study day or relative day for a visit is defined as:

- Visit date date of Day 1 +1, if visit date ≥date of Day 1
- Visit date date of Day 1, if visit date <date of Day 1

There is no 'Day 0'

Study Day is calculated in reference to the date of randomization for efficacy analyses and date of first dose for safety analyses (efficacy analysis Study Day 1 = date of randomization; safety analysis Study Day 1 = date of first dose). Positive study days will count forward from Study Day 1. Study Day -1 will be the day before Study Day 1, and all subsequent negative study days will be measured backward from Study Day -1.

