5.4.2. Analysis Methods

Exploratory time to event variables will be analyzed descriptively only for apalutamide group. KM method will be applied to graphically describe the distribution. Median event times, the 6-month,

1-year and 2-year event free rates, as appropriate, and their 2-sided 95% confidence intervals will be provided.

SAFETY

Safety data will be analyzed using safety analysis set. The safety parameters to be evaluated are the incidence, intensity, and type of adverse events (AE), vital signs, ECG, and clinical laboratory results.

Unless otherwise specified, no statistical inference will be performed in analyzing the safety data.

In this study, control group subjects without distant metastasis will switch to treatment with apalutamide plus ADT after completion of 5 cycles of placebo + ADT treatment (handling by the IWRS). Subjects who have documented PSA progression prior to completion of 5 cycles of study treatment, will cross over to apalutamide at the time of PSA progression. As such, safety data will be presented by the following treatment groups as appropriate.

Placebo ^a	Apalutamide	Placebo to Apalutamide b	Apalutamide Treated ^c

^a Placebo subjects treated with Placebo + ADT before cross-over

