6.1. Adverse Events

Subjects will be assessed for adverse events while on the study. Adverse events (AEs) will be graded according to the NCI Common Terminology Criteria for Adverse Events (CTCAE) version 4.03 and coded to preferred term and system organ class (SOC) using the MedDRA version 20.0 or later. All AEs reported on or after the date of first dose until 30 days (inclusive) after the last dose of study drug will be considered treatment-emergent and will be summarized by treatment group.

For each treatment group, AE incidence rates will be summarized with frequency and percentage by SOC and preferred term, with all subjects treated in that treatment group as the denominator, unless otherwise specified. In addition, AE incidence rates will also be summarized by severity and relationship to study drug. Treatment-related AEs are those judged by the Investigator to be at least possibly related to the blinded study drug. AEs with missing severity or relationship to study drug will be classified as severe and treatment-related, respectively. Subjects with multiple occurrences of events will only be counted once at the maximum severity to study drug for each preferred team, SOC. Deaths that occur within 30 days after the last dose of study drug are defined as on-study deaths.

Summary tables of the following AEs will be provided:

Overall summary of AEs: the number and percentage of subjects who experienced any AE including COVID-19, number of subjects with Grade 3/4 AEs, any serious adverse event

22

^b Placebo subjects treated with apalutamide + ADT after cross-over

^c Subjects treated with apalutamide + ADT including subjects from original apalutamide arm and subjects crossed over from placebo arm

(SAE) including COVID-19, any treatment-related AE, treatment related Grade 3/4 AE, any treatment-related SAE, AE leading to treatment discontinuation including COVID-19, related AE leading to treatment discontinuation, AE leading to death including COVID-19, related AE leading to death, and all deaths within 30 days of last dose

- All AEs by SOC and preferred term
- All AEs by SOC, preferred term, and toxicity grade
- Grades 3 or 4 AEs by SOC and preferred term
- Grades 3 or 4 AEs by decreasing frequency of preferred term
- Treatment-related AEs by SOC and preferred term
- Treatment-related AEs by SOC, preferred term, and toxicity grade
- Treatment-related AEs by decreasing frequency of preferred term

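### Partial AE onset dates are anchored to Cycle 1 Day 1 only, so in placebo participants an AE that arose on apalutamide can be dated before the cross-over and counted under placebo

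*SAP*

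**What the plan says.** SAP 2.7 has one set of onset rules. They use study drug start, calendar defaults and, in some branches, the AE resolution date:

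- Day missing, onset outside the month of study drug start: "First day of the month that the AE occurred, if month/year of the onset of AE is different".
- Day missing, onset inside that month: "The day of study drug start, if the month/year of the onset of AE is the same as month/year of the study drug start date". If the AE also resolved in that month, the earlier of drug start and resolution is used.
- Day and month missing: the earliest of several candidates. These include "January 1 of the year of onset, as long as this date is on or after the study drug start date", the drug start date if it lies in the onset year, and the resolution date.
- Onset date wholly missing: no imputation.

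SAP 2.7 does not define study drug start. SAP 2.5 says "Study Day 1 or Day 1 refers to the start of the first study drug administration for safety analysis", and SAP 2 says "The first dose starts on Day 1 of Cycle 1". For a placebo participant, that is the first placebo dose. SAP 2.7 mentions neither the cross-over date nor the first apalutamide dose after placebo.

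The SAP safety section (ahead of 6.1) then sets out four columns. Its footnotes define the placebo column as "Placebo subjects treated with Placebo + ADT before cross-over" and the placebo-to-apalutamide column as "Placebo subjects treated with apalutamide + ADT after cross-over". A further column pools everyone treated with apalutamide. Neither the SAP nor Protocol 9.3.2 says how an AE with a partial date is placed on one side of the switch.

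**The concern.** Cross-over is built into the design. Every placebo participant without distant metastasis moves to apalutamide at PSA progression or after 5 cycles, so each contributes AEs to two columns and the onset date is needed to choose between them. An imputation anchored only to the first placebo dose ignores that boundary. When the known part of the date spans the switch, the imputed date falls at the start of the interval, on placebo.

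This runs against the SAP's other conventions, which lean towards the drug. An AE in the first-dose month is dated no earlier than drug start unless it resolved before then, and SAP 6.1 classes missing severity as severe and missing relationship as related. At the first apalutamide dose of a placebo participant, the same rules lean the other way. Safety and tolerability of apalutamide is a secondary objective. The shift adds AEs to the placebo column and removes them from the placebo-to-apalutamide and pooled apalutamide columns.

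**Working it through.** The plan states no figure on this point, so there is nothing to reproduce. The check applies the SAP 2.7 rules to the calendar.

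**Inputs**
- Cycle length 28 days; cross-over at the latest after 5 cycles, that is day 140 after Cycle 1 Day 1 (Protocol 4.1).
- Earliest visit named for dispensing active drug after PSA progression: Cycle 3 Day 1, day 56 (Protocol 1.3, footnote 8).
- First-dose dates taken as 1 February 2020 to 31 October 2022, from the accrual dates in the Amendment 3 rationale: 1,004 dates.
- About 25 placebo participants (Protocol 4.2.1).
- Assumed: first-dose dates and onset days uniform; no resolution date overrides the result.

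**Step 1: which branch applies.** Day 56 is longer than any calendar month, so cross-over never falls in the first-dose month (0 of 1,004 dates at days 56, 84, 112 and 140). A missing-day AE in the cross-over month is therefore always set to the 1st.

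**Step 2: where the 1st falls.** It precedes cross-over unless cross-over is itself on the 1st: 33/1,004 = 3.3% of dates. With cross-over at day 140, the cross-over months contain 15,788 possible onset days on apalutamide and 14,773 on placebo.
- Apalutamide-onset days dated before the switch: 14,784/15,788 = 93.6% (93.6% to 93.7% at the other timings).
- Placebo-onset days dated on or after the switch: 0.

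**Step 3: year-only dates.** For an AE that arose on apalutamide in the calendar year of cross-over, the imputed date precedes the switch in 99.4% to 99.6% of cases.

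**Example.** First dose 10 March 2021; 140 days later is 28 July 2021. True onset 30 July, recorded as July 2021. The imputed date is 1 July, in the placebo period. Recorded as 2021 only, it becomes 10 March, also in the placebo period.

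**Step 4: size.** Expected misplaced AEs = participants × AEs per man in the cross-over month × share after the switch × share with a partial date. A share of one half is in line with Step 2: 15,788/(15,788 + 14,773) = 0.52. One AE per man and the partial-date range are assumptions; the documents give neither.
- At 1%: 25 × 1 × 0.5 × 0.01 = 0.125
- At 5%: 25 × 1 × 0.5 × 0.05 = 0.625
- At 10%: 25 × 1 × 0.5 × 0.10 = 1.25

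The formula covers the missing-day case only. Allowing for switches on the 1st would lower each figure by about 6%.

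**Step 5: effect on a table row.** One man in the placebo column is 1/25 = 4 percentage points. SAP 6.1 counts a man once per preferred term and system organ class, so 4 points is a ceiling. It is reached only if he has no other placebo-period AE in that row.

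**The case against.** **Two steps are inferred.** SAP 2.7 says study drug start, not first study drug administration, and no sentence says the imputed date decides the column. This stands as a limit. But SAP 2 and 2.5 supply the only start date available, and the columns cannot be filled without a date. If the sponsor uses another rule, the SAP does not state it.

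**Few dates will be partial.** Visits fall on Day 1 of each 28-day cycle through Cycle 6, and data are queried and checked against source. That favours the lower end of the range and stands. Similarly, the protocol reports a median of 82 days to first rash in the pivotal study. Men have on average about 16 apalutamide days in the cross-over month, so if that median carries over, most first rashes would fall outside the missing-day window.

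**A new anchor only reverses the error.** Partly true: AEs that began on placebo and were unresolved at the switch would move to apalutamide. It is a choice between conventions. The reverse one is conservative for the drug under study and matches how the SAP treats the first-dose month.

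**Stronger readings.** A reader might infer that every misplaced AE costs 4 percentage points; the once-per-row counting rule makes that a maximum. A reader might also infer that the trial's safety comparison is unreliable. The documents do not support that: the column of men randomised to apalutamide is untouched, safety is descriptive with no inference planned, and the primary endpoint does not use AE dates.

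**Conclusion.** The gap is real and minor. Followed as written, and if the imputed date decides the column, SAP 2.7 dates nearly all partial-date AEs that arose on apalutamide in the cross-over month (or, for year-only dates, the cross-over year) to the placebo period, and moves none the other way. The direction follows from the text. The size does not, because it depends on AE and partial-date rates that the documents do not give. Under the stated assumptions it is about 0.1 to 1.3 AEs among about 25 men, with at most 4 percentage points per AE in a placebo-column row. Only descriptive safety tables are affected. AEs with a known day, or with a partial date clearly on one side of the switch, are handled correctly now.

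**What to change.** Add to SAP 2.7: for placebo participants who crossed over, if the known part of the onset date equals the month and year of the first apalutamide dose (or the year, when the month is also missing), and the AE did not resolve before that dose, onset is set to the date of the first apalutamide dose. All other partial dates follow the existing rules. Also state that the imputed onset date determines the safety column.

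The restriction to a matching month or year matters. A rule covering any partial date compatible with onset after the switch would pull an onset recorded as November 2021 back to a 28 July 2021 cross-over, although the present rule already places it correctly on 1 November.

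The cost is two sentences and a small programming change. The downside is that some placebo-onset AEs unresolved at the switch will be attributed to apalutamide, and for year-only dates this can reach back over the whole placebo period in that year. The SAP should acknowledge this as the conservative choice.

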3. INTERIM ANALYSIS AND DATA MONITORING COMMITTEE REVIEW

3.1. Independent Data Monitoring Committee (IDMC)

An IDMC was commissioned to review the efficacy and safety data at the originally planned interim analysis prior to Protocol Amendment 3 (PA3). Per PA3, interim analysis is no longer applicable and the study will be unblinded at the final analysis when 75 subjects completed 5 cycles of study treatment. However, the IDMC will continue to be engaged to ensure that they are informed of any potential safety issue or emerging data. The IDMC will help review final analysis results and may provide recommendations to the sponsor regarding study conclusions or further analyses. Complete details regarding the IDMC responsibilities, authorities, and procedures will be documented in the IDMC charter.

3.2. Interim Analysis for Efficacy

No interim analysis is planned for this study.

4. SUBJECT INFORMATION

4.1. Demographics and Baseline Characteristics

The following parameters will be summarized by treatment group using the ITT analysis set:

- Age, race, ethnicity, weight, height
- ECOG performance status
- Baseline PSA value and PSA Doubling Time (PSADT)
- Time (months) from initial diagnosis of prostate cancer to randomization
- Total Gleason Score at initial diagnosis
- Tumor stage at initial diagnosis
- Lymph nodes stage at initial diagnosis
- Number of prior hormonal therapies
- History of surgical prostate cancer procedures (Yes/No)
- Type of surgical procedures (prostatectomy, orchiectomy, transurethral resection of the prostate (TURP), and other)
- History of radiotherapy (Yes/No)
- Type of radiotherapy
- History of prior chemotherapy (Yes/No)

4.2. Disposition Information

The number and percentage of subjects who are screened, screen failed, enrolled (randomized), dosed, or have study or treatment early terminated as well as the reason for discontinuation (including COVID-19 related) will be summarized by treatment group using ITT analysis set.

4.3. Treatment Compliance

Treatment compliance and dose modifications will be summarized by treatment group using the safety analysis set.

Treatment duration will be defined as the duration of time from the date of the first dose of study drug to the date of last dose of study drug + 1 day.

Drug compliance will be summarized by the treatment group and the percent treatment compliance will be defined as the number of tablets taken during the study divided by the expected number of tablets, multiplied by 100. The number of tablets taken will be calculated based on the number of tablets dispensed minus the number of returned tablets. A subject's expected number of tablets will be calculated according to the planned treatment regimen. For example, for subjects with no dose modification the expected number of tablets equals the number of assigned tablets per day multiplied by treatment duration, however for subjects with dose reduction the expected number of tablets will be smaller. Subjects with at least one dose reduction or with dose interruption and the reason for the dose modification will be summarized by treatment group.

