1.3. Schedule of Activities (SoA)

	Comments	Prescreening ¹	Screening		Treatment Phase (One cycle = 4 w	eeks [28 days	:]) ²	Posttreatment follow-up ³
Activities and Forms to be Completed			≤35 Days Prior to Randomization	Cycle 1 Day 1	D1 C1-C6, D1 of every 2 cycles starting at C7 to C13, then D1 of every 4 cycles, unless otherwise specified	Every 4 cycles	End-of- Treatment (~ 30 days of the last dose of study treatment)	
Screening								
Informed Consent		X	X					
Medical/Oncological History			X					
Inclusion/Exclusion Criteria ⁴			X					
Randomization	Participants will be randomly assigned to the treatment arms; randomize no more than 1 week before dosing.		х					
Study Drug Administration								
Apalutamide/Matched Placebo Administration ⁵	C1D1 must be within 1 week of randomization			X	X			
Study Drug Compliance					X		X	
Laboratory Studies								
Hematology			X	X	X		X	
Serum Chemistry panel/tests			X	X	X		X	
Testosterone			X	X		X	X	
Thyroid Stimulating Hormone ⁶			X	X		X	X	
Fasting Lipid Panel			X	X		X	X	
HBsAg, anti-HCV			х					
HBV-DNA and HCV-RNA			X ⁷					
Efficacy								
Serum PSA Evaluation	During treatment phase: Blinded; submit to central lab	х	X	х	X ⁸		Х	
CT brain			X ⁹					

 $\label{eq:confidential} \textbf{CONFIDENTIAL} - \textbf{FOIA} \ \textbf{Exemptions} \ \textbf{Apply} \ \textbf{in} \ \textbf{U.S.}$

	Comments	Prescreening ¹	Screening		Treatment Phase (One cycle = 4 w	eeks [28 days	[j] ²	Posttreatment follow-up ³
Activities and Forms to be Completed			≤35 Days Prior to Randomization	Cycle 1 Day 1	D1 C1-C6, D1 of every 2 cycles starting at C7 to C13, then D1 of every 4 cycles, unless otherwise specified	Every 4 cycles	End-of- Treatment (~ 30 days of the last dose of study treatment)	
CT chest, abdomen, and pelvis ¹⁰	May occur up to 8 days before cycles requiring images. Unscheduled assessments can occur at any time as needed if signs of disease progression are observed.		Xº			х	x	х
Bone scans	May occur up to 8 days before cycles requiring images. Unscheduled assessments can occur at any time as needed if signs of disease progression are observed.		X9			Х	x	X
Survival and SREs				X	X	X	X	X
Subsequent anticancer therapy				X	X	X	X	Х
Safety								
Physical Examination	The screening physical examination will also include a full review of medical or oncological history and a complete examination of all organ systems. Limited symptom directed physical examinations and weight assessment will be conducted at other visits.		x	x	x		x	

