Study intervention should be dispensed under the supervision of the investigator or a qualified member of the study-site personnel, or by a hospital/clinic pharmacist. Study intervention will be supplied only to participants participating in the study. Returned study intervention must not be dispensed again, even to the same participant. Whenever a participant brings his study intervention to the study site for pill count, this is not seen as a return of supplies. Study intervention may not be relabeled or reassigned for use by other participants. The investigator agrees neither to dispense the study intervention from, nor store it at, any site other than the study sites agreed upon with the sponsor.

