6.4. Study Intervention Compliance

At each clinic visit, participants will be asked to return any remaining study drug from the previous dosing cycle as well as all used and unused study drug containers.

Treatment compliance will be defined as the number of tablets taken divided by the expected number of tablets and reported as percentage. In case of dose reductions, the expected number of tablets will reflect the new dose level. Tablets that are not returned will be considered to have been taken, unless otherwise specified in the eCRF.

The investigator or designated study site personnel will be responsible for providing additional instruction to any participant who is not compliant with taking the study drug. In the absence of toxicity, if the dosing compliance is not 100%, then investigators or designated study site personnel should re-instruct participants regarding proper dosing procedures and the participant may continue study treatment.

The study site must maintain accurate records demonstrating dates and amount of study drug received, to whom dispensed (participant-by-participant accounting), and accounts of any study drug accidentally or deliberately destroyed. At the end of the study, reconciliation must be made between the amount of study drug supplied, dispensed, and subsequently destroyed or returned to sponsor or its representative.

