Subjects will be followed for safety and efficacy as per the schedule of activities and will remain on study treatment until development of distant metastases as assessed by investigators or the development of unacceptable toxicity or the study end defined as MFS events observed in approximately 60% of the study population or 3 years after the final analysis for the primary endpoint TTPP, whichever comes first. An End of Treatment (EoT) Visit will occur approximately 30 days of the last dose of study treatment. The Post-treatment Follow-up Phase will begin after the EoT visit. Subjects will be contacted every 4 months to obtain survival status, recording of development of symptomatic progression, initiation of any new systemic anti-cancer therapies until death, withdrawal of consent for study participation, or termination of the study. The final analysis for the primary endpoint TTPP will occur at 5 months after the last subject received the first dose.

Figure 1

Note: ADT: androgen deprivation therapy, being either surgical castration or gonadotrophin-releasing hormone agonists (GnRHa), will be continued as background therapy for all subjects. ADT with GnRHa will be continued for all patients who have not been surgically castrated.

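### SAP 4.3 counts supply not yet due for return as taken, so compliance is overstated for men still on treatment at the final TTPP analysis

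*SAP*

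**What the plan says.** For the numerator, SAP 4.3 states: "The number of tablets taken will be calculated based on the number of tablets dispensed minus the number of returned tablets". For the denominator, with no dose modification, "the expected number of tablets equals the number of assigned tablets per day multiplied by treatment duration", and treatment duration is the time "from the date of the first dose of study drug to the date of last dose of study drug + 1 day". SAP 4.3 has no rule for tablets still at home at a data cut, no definition of last dose for a man who has not stopped, and no cap at 100%.

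Protocol 6.4 has a similar rule with an exception: "Tablets that are not returned will be considered to have been taken, unless otherwise specified in the eCRF". SAP 4.3 does not repeat the exception.

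Returns are tied to visits. Protocol 6.4 says "At each clinic visit, participants will be asked to return any remaining study drug from the previous dosing cycle", and Protocol 6.2 adds "Whenever a participant brings his study intervention to the study site for pill count, this is not seen as a return of supplies". In the Protocol 1.3 Schedule of Activities, study drug administration falls in the column headed "D1 C1-C6, D1 of every 2 cycles starting at C7 to C13, then D1 of every 4 cycles, unless otherwise specified". Visits are therefore 1 cycle apart up to Cycle 7, 2 cycles apart up to Cycle 13, and 4 cycles apart afterwards.

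On timing, SAP 1.2 states: "The final analysis for the primary endpoint TTPP will occur at 5 months after the last subject received the first dose". No interim analysis is planned (SAP 3.2). Men without metastasis or unacceptable toxicity may stay on treatment for up to 3 years after that analysis (SAP 1.2).

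**The concern.** Numerator and denominator cover different periods. For a man who has stopped and handed back his leftovers, they agree. For a man still on drug at the cut, the numerator includes everything dispensed at his last visit, including tablets meant for days after the cut. The denominator ends at his last dose.

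Adherent men would be shown above 100%, and some poorly adherent men would look acceptable. The error depends on the dispensing interval and on time since first dose, so it differs between men and possibly between columns. SAP Section 6 plans, as appropriate, separate safety columns for placebo before cross-over and for apalutamide-treated time. If compliance is laid out that way, the placebo column covers at most 5 cycles with visits 1 cycle apart. Part of any difference between columns would then be an artefact of the accounting.

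**Working it through.** The documents state no compliance figure, so there is none to reproduce. The check applies the SAP 4.3 rule to the visit schedule.

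**Inputs from the documents**
- Cycle length: 28 days (Protocol 1.1).
- Visits in days after first dose: 0, 28, 56, 84, 112, 140, 168, 224, 280, 336, then every 112 days (Protocol 1.3).
- Accrual 32 months plus 5 months of follow-up (Protocol 9.1), so time since first dose at the cut is 5 to 37 months. At 30.4375 days per month this is 152.2 to 1126.2 days, a span of 974 days.
- Median apalutamide exposure in the earlier pivotal study: 32.9 months (Protocol 2.2). It is used only to model men who have stopped.

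**Assumptions**
- Follow-up is uniform over that range.
- Each supply lasts exactly to the next scheduled visit.
- Earlier supplies are fully accounted for.
- The one-day inclusive count is ignored.

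**Formula.** For a fully adherent man at day t, with next visit at day v, shown compliance = v / t if duration ends at the cut.

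**Single cases**
- Just after Cycle 7 Day 1: 224/168 = 133%.
- Just after Cycle 13 Day 1: 448/336 = 133%.
- At 12 months: 448/365.25 = 123%.
- Just before any visit: 100%.

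**Average over men on drug, duration to the cut.** Each stretch from a to b within one visit interval contributes v × ln(b/a). In days:
- 152.2–168: 168 × ln(168/152.2) = 16.6
- 168–336, three 2-cycle intervals: 64.4 + 62.5 + 61.3 = 188.2
- 336–1120, seven 4-cycle intervals: 128.9 + 125.0 + 122.5 + 120.9 + 119.6 + 118.7 + 118.0 = 853.6
- 1120–1126.2: 1232 × ln(1126.2/1120) = 6.8

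The sum is about 1065, and 1065/974 = 1.094, or 109.4% on average. The median is 108.1%, and 39% of these men exceed 110%. The current supply is 1 cycle for 2% of them, 2 cycles for 17% and 4 cycles for 81%.

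**Duration ending at the last visit.** Shown compliance becomes v divided by the last visit day. The mean is 120.2% and the maximum is again 133%.

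**Over all men.** With exponential discontinuation at rate L = ln2/32.9 per month, the share still on drug is (e^(−5L) − e^(−37L))/(32L) = (0.900 − 0.459)/0.674 = 0.65. Men who have stopped add no excess. With duration to the cut, the mean excess over all men is 6.5 points. With assumed medians of 20 and 45 months it is 5.3 and 7.2.

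**A man who truly takes 80%.** His earlier leftovers are returned, but his open supply counts in full. He is shown at 91.1% on average (duration to the cut).

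**Placebo period.** Five cycles are 5 × 28 = 140 days. This is less than the 152.2 days that the last participant has been followed at the cut. On schedule, every placebo supply has therefore been closed by cross-over or discontinuation, and the excess is near zero.

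**The case against.** The strongest reply is that this is an undefined detail in a descriptive table, and that no size can be attached to it. Several parts of that reply stand.

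- **Supply size is inferred.** The Schedule of Activities gives visit timing, but no section states the quantity dispensed per visit.
- **No single number is secure.** A reader might take 9 points as the average error and 33 as its ceiling. The documents support neither as a fact. The average moves between about 5 and 20 points with the definition of last dose and with who is averaged. The 33 is also not a ceiling: if one full 120-tablet bottle per 28-day cycle is counted, the maximum is 35.7 points. If time after cross-over is scored alone from day 140, it is about 200 points just after Cycle 7 Day 1 (56 surplus days over 28 days).
- **The analysis time is partly inferred.** SAP 1.2 times the final TTPP analysis, and the study continues after it. Protocol 6.4 requires drug reconciliation at the end of the study, and once supplies are closed the problem disappears. It remains for any compliance table produced at the final TTPP analysis.
- **The eCRF exception is not revoked.** A reader might infer that the SAP overrides Protocol 6.4. It only fails to repeat the exception. Even with the exception, nothing says how to treat supply that is simply not yet due back.
- **Compliance is not the only evidence of treatment taken.** A reader might infer that the treatment comparison is undermined. The plan also reports exposure from dosing records (SAP 4.4), dose modifications (SAP 4.3), deviations for wrong treatment or incorrect dose (SAP 4.5) and plasma concentrations (SAP 7). Efficacy uses the ITT set (SAP 2.3.1), and no test, analysis set or censoring rule uses compliance.

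The reply does not remove the mismatch. SAP 4.3 states a rule, and applied as written it counts open supply as taken.

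**Conclusion.** The point holds as a definition that overstates compliance for men still on treatment at the final TTPP analysis. On the cases checked, the bias is upward or zero.

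A fully adherent man still on drug is shown at about 109% on average (100% to 133%) if duration ends at the cut, and about 120% if it ends at his last visit. Over all men the excess is about 5 to 7 points if some have stopped and duration runs to the cut. These figures rest on uniform accrual and on supply lasting to the next scheduled visit.

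The placebo period is little affected. If it has its own column, part of any difference between columns would be an artefact. The TTPP test is unaffected. The change is worth making because it is cheap and corrects a figure that will be reported.

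**What to change.** In SAP 4.3:

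1. Compute compliance over dispensing intervals closed by a later accountability visit (next dispensing, pill count or End-of-Treatment visit) on or before the data cut, whether or not any tablets came back. Requiring a recorded return would be wrong: it could drop intervals with nothing left over, and intervals that were only pill-counted, which Protocol 6.2 does not class as returns.
2. Use the same intervals for tablets taken and expected tablets, and leave the open interval out of both.
3. Subtract tablets that the eCRF records as lost or not taken, in line with Protocol 6.4. Tablets counted at a pill count but kept by the participant should be treated as not yet taken.
4. Define the date of last dose for men still on treatment at the cut.

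Under this rule a fully adherent man scores 100%, and a man who takes 80% scores 80%. The cost is SAP wording and minor programming on accountability data already collected. The last open interval of each ongoing man, up to 4 cycles, is not described.
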